- 15. Current or recurrent urinary tract infection (3 or more infections in the last 6 months), or presence of urinary fistula, or urinary tract obstruction such as cancer, urethral stricture or presence of urinary stone
- 16. History of chemotherapy or pelvic radiotherapy that might have affected bladder control or caused neuropathies (i.e. peripheral neuropathy).
- 17. Uterine prolapse, cystocele, enterocele or rectocele with pelvic prolapse beyond the hymen.
- 18. Other active implantable electronic device/s regardless of whether stimulation is ON or OFF.
- 19. Have a life expectancy of less than 1 year.
- 20. Subjects who are breastfeeding.

SAMPLE SIZE CONSIDERATION

Sample size calculation, based on the primary endpoint, yields a sample size of 114 patients. This calculation assumes an underlying response rate of 65%, the null response rate (performance goal) of 50%, with power of 90% and one-sided significance level of 0.025. To account for up to 15% attrition, a total of 134 subjects would be required. However, the total sample size of 150 subjects is driven by an important secondary objective that is expected to be evaluable in 70% of enrolled subjects: The proportion of responders at 6 months post system activation as

Number	Revision / Date	Page
G02-CLP-0002_US	Rev. 08 / 27 July 2021	19 of 75

	demonstrated by ≥50% improvement in the average number of moderate-severe urgency episodes PPIUS degree 3,4 or <8 voids/day. The assumed underlying response rate is 61%, with performance goal of 45%, 85% power and one-sided significance level of 0.025 yields a sample size of 89 subjects. To account for up to 15% attrition, 105 subjects are required to meet the criteria for this objective. Assuming 70% of enrolled subjects meet the criteria, a total of 150 subjects are required to be enrolled.
STATISTICAL ANALYSIS	For the primary endpoint, the lower 95% Clopper-Pearson confidence bound on the overall success rate will be calculated and compared to a pre-specified performance goal. Success on the primary analysis will be declared if the lower confidence bound is greater than the performance goal of 50%.

Number	Revision / Date	Page
G02-CLP-0002 US	Rev. 08 / 27 July 2021	20 of 75

5. Introduction

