13.4 Sample Size Considerations

The sample size was calculated using PASS 2015 software by a one-sided exact test for a single binomial population, under the following assumptions:

- Significance level = 0.025 (one-sided)
- Power ≥ 90%
- Assumed treatment success rate = 65%
- Prespecified performance goal = 50%.

Given these assumptions, 134 evaluable subjects would be required to participate in the trial, taking into account an assumed attrition rate of 15%.

The total sample size for this trial, however, is driven by an important secondary objective:

To demonstrate the proportion of responders at 6 months post system activation, defined by ≥50% improvement in the average number of moderate-severe urgency episodes PPIUS degree 3,4 or <8 voids/day, is greater than 45%. A total of 89 evaluable subjects are required. Assuming 15% attrition rate, a total of 105 subjects meeting the criteria described above is needed. With 70% of enrolled subjects meeting the analysis criteria, 150 total sample size is sufficient to evaluate the secondary endpoint.

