7.1 ITT population

Treatment of missing values:

- Subjects missing data "not in random" will be imputed as "failure" on dichotomous endpoints.
- "Failures" (not MAR) include:
 - Subject leaves the study due to related AE
 - Device explant
 - o Lack of effect that results in significant increase of UUI medication
 - Need for other 3rd line therapies for the management of UUI

Document ID	Revision / Date	Page
G02-CLP-0009	Rev. 06 / 18 May 2022	11 of 26

- Baseline values will not be imputed
- Missing values in ITT not due to "failure" will be imputed using multiple imputation (MI).

Multiple imputation will be applied to the primary and three secondary endpoints. The 'additional endpoint' analyses will not use multiple imputation. The imputation procedure will be performed on the continuous outcomes (e.g. number of incontinence episodes). Based on the imputed continuous outcome, the response will be defined accordingly for each endpoint.

The hypotheses will be tested by performing the logistic regression on each imputed dataset. Then SAS PROC MIANALYZE procedure will be used to calculate the combined confidence interval and the corresponding p-value. The evaluation on each endpoint will be successful if the lower limit of the confidence interval is above 50%. In addition, the primary analysis will present the observed frequency of responders and descriptive statistics of response rates over all imputed datasets.

Fifty (50) imputed datasets will be created (the seed is set to 123456).

The imputation will be done using covariates: Age, BMI, average number of urgency leaks, average number of urgent voids, HRQL score and OAB duration at baseline. This list might be reduced if the model fails to converge.

Because MI assumes missing at random (MAR), sensitivity analyses (i.e. tipping point) described below, will be conducted to test the effects of other patterns of missingness.

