This endpoint is defined only for patients with baseline number of voids per day of at least 8 and baseline number of urgent episodes (PPIUS 3 or 4) of at least 9 per 7-day diary. It is expected that 70% of enrolled subjects will meet these criteria.

Sample size requirements to evaluate this secondary endpoint are calculated in the same manner as the primary, under the following assumptions:

- Significance level = 0.025 (one-sided)
- Power ≥ 85%
- Assumed treatment success rate at 6 months = 61%
- Prespecified performance goal = 45%

A total of 89 evaluable subjects are required. Assuming 15% attrition rate, a total of 105 subjects meeting the criteria described above is needed. With 70% of enrolled subjects meeting the analysis criteria, 150 total sample size is sufficient to evaluate the secondary endpoint.

The total sample size for the OASIS trial is 150 subjects.

10 Data Derivation and Transformation

Data not specifically recorded on a CRF will be derived as follows:

- Study Duration [days] = Date of Last Visit Date of First Visit + 1.
- HbA1c values will be reported in units of mmol/mol. For cases of HbA1c reported in percentage, the following conversion formula will be used:

Document ID	Revision / Date	Page
G02-CLP-0009	Rev. 06 / 18 May 2022	16 of 26

HbA1c (mmol/mol) = $[HbA1c (\%) - 2.15] \times 10.929^{1}$

- Coding of Adverse Events will be done using the most recent MedDRA version.
- Coding of Concomitant Medication will be done using the most recent WHO Drug dictionary version.
- Baseline will be defined as the value at the "Enrollment and Screening" visit unless noted otherwise.
- OAB duration at baseline from Date of OAB Diagnosis [years] = Date of Screening Date of OAB Diagnosis/365.25.
- Partial dates that are required for analysis will be imputed in the following fashion:
 - o Dates with missing month and day will be imputed as July 1st.
 - o Dates with missing day only will be imputed as the 15th of the month.
- Since querying of paper diaries is not possible at the time of completion and not feasible in an accurate
 manner afterwards, no query management process is used for the paper diaries. In its place a set of
 automatic rules will be applied to correct discrepancies in the paper diaries, as detailed in the appendix
 to the SAP.

11 Interim Analysis

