12.6.2 Secondary Efficacy Analysis

The following secondary efficacy analyses will be carried out using the ITT, PP and OR1 populations:

- The analysis carried out as the primary efficacy analysis will be repeated on the PP and OR1 populations.
- The secondary endpoints will be presented according to the following performance goals stated for each:
 - Proportion of subjects with ≥10 points (MID) improvement compared to baseline in HRQL (based on OAB-q) at 6 months post system activation with PG of 50%.
 - Proportion of responders at 12 months post system activation as demonstrated by ≥50% improvement in either average number of urgency related incontinence episodes or average number of large (severe) urgency related incontinence episodes, as measured by 7-day Patient Voiding Diary, with PG of 50%.
 - Proportion of responders at 6 months post system activation as demonstrated by ≥50% improvement in the average number of moderate-severe urgency episodes PPIUS degree 3,4 or <8 voids/day with PG of 45%.

Hypothesis testing for the secondary endpoints will be performed in the same manner described for the primary endpoint with respect to multiple imputation. Success on each of the secondary endpoints will be declared if the lower bound of this confidence interval is above the stated performance goal.

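### SAP 7.1 gives every tested endpoint a 50% success limit, contradicting the 45% performance goal set for the PPIUS/voids secondary endpoint

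*SAP*

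**What the plan says.** SAP 7.1 sets its scope first: "Multiple imputation will be applied to the primary and three secondary endpoints". It then describes logistic regression on each imputed dataset, pooling with PROC MIANALYZE to obtain a confidence interval and p-value, and one success rule: "The evaluation on each endpoint will be successful if the lower limit of the confidence interval is above 50" percent. No endpoint is excepted.

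For the PPIUS/voids endpoint the other sections give a different figure:

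- SAP 12.6.2 lists it as "moderate-severe urgency episodes PPIUS degree 3,4 or <8 voids/day with PG of 45" percent.
- SAP 9 sizes it with "Prespecified performance goal = 45" percent.
- Protocol 13.4 states the objective as a responder proportion for "moderate-severe urgency episodes PPIUS degree 3,4 or <8 voids/day, is greater than 45" percent.
- The protocol synopsis says: "The assumed underlying response rate is 61%, with performance goal of 45%, 85% power and one-sided significance level of 0.025".

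SAP 12.6.2 also has its own success rule: "Success on each of the secondary endpoints will be declared if the lower bound of this confidence interval is above the stated performance goal". The primary endpoint and the other two secondaries (HRQL at 6 months, leak response at 12 months) have 50% goals, so for them 7.1 and 12.6 agree.

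**The concern.** Two current sections of the same SAP set different pass marks for one formally tested endpoint. Over a band of plausible results one section declares success and the other failure. This endpoint is also the documents' stated reason for enrolling 150 subjects rather than the 134 needed for the primary. Power lost on it is power that the extra enrolment was meant to secure.

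There is a related gap. SAP 7.1 takes a p-value from the pooled logistic regression without stating its null value. By default an intercept is tested against zero, and a logit of zero is a proportion of 50%. If that default were left in place, the p-value entering the Hochberg procedure (SAP 12.6.2.1) would test 50% even if the confidence limit were compared with 45%.

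**Working it through.** **Inputs.** From SAP 9 and the protocol synopsis: assumed rate 61%, goal 45%, one-sided alpha 0.025, power 85%, 89 evaluable, 15% attrition, 70% of enrolled subjects qualifying, 150 in total. From SAP 7.1: limit 50%.

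**Step 1: reproduce the plan's figure.** For the exact one-sided binomial test, take the smallest r with P(X ≥ r | n, p0) ≤ 0.025; power is P(X ≥ r | n, 0.61). With n = 89 and p0 = 0.45, r = 50, attained alpha is 0.0223 and power is 85.1%. No smaller n reaches 85%. Then 89/0.85 = 104.7, rounded up to 105, and 105/0.70 = 150. The plan's sizing therefore rests on the 45% goal. Against 50%, 85% power would need at least 186 evaluable; 186/0.85 = 218.8, so 219; 219/0.70 = 312.9, so 313 enrolled.

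**Step 2: apply each limit.** Two lower limits of a two-sided 95% interval were used:

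- Exact (Clopper-Pearson), which gives the same critical values as the exact test.
- Logit-scale Wald, closer to the SAP's logistic regression: L = ln(r/(n−r)) − 1.96·√(1/r + 1/(n−r)), back-transformed as 1/(1+e^(−L)).

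Wald example at n = 89. For r = 54, ln(54/35) = 0.4336 and the standard error is 0.2170, so L = 0.0083 and the lower limit is 0.502, just above 50%. For r = 53 the lower limit is 0.491, which fails.

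Both 89 (after attrition) and 105 (150 × 0.70, no loss) are shown, with a true rate of 61%:

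| n | Method | Minimum successes, 45% | Power | Minimum successes, 50% | Power | Pass 45%, fail 50% | Chance of that band |
|---|---|---|---|---|---|---|---|
| 89 | Exact | 50 | 85.1% | 55 | 48.5% | 50–54 | 36.6% |
| 89 | Logit Wald | 50 | 85.1% | 54 | 57.1% | 50–53 | 28.0% |
| 105 | Exact | 58 | 90.4% | 64 | 54.7% | 58–63 | 35.8% |
| 105 | Logit Wald | 58 | 90.4% | 63 | 62.4% | 58–62 | 28.0% |

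The last column is the difference between the two powers, taken before rounding.

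**Step 3: direction of the error.** At n = 89 and a true rate of 45%, the exact chance of success is 2.2% under the 45% limit and 0.1% under the 50% limit. The literal 7.1 rule is stricter.

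**Step 4: the p-value.** Take 50/89. The logit is ln(50/39) = 0.2485 with standard error √(1/50 + 1/39) = 0.2136.

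- Against logit(0.45) = ln(0.45/0.55) = −0.201: z = (0.2485 + 0.2007)/0.2136 = 2.10, two-sided p = 0.036.
- Against zero: z = 0.2485/0.2136 = 1.16, two-sided p = 0.245.

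To illustrate the effect in Hochberg, suppose the other two secondaries each had p = 0.04 (an assumed value). With 0.036 the largest p is 0.04, below 0.05, and all three are rejected. With 0.245 the largest fails at 0.05, the next (0.04) exceeds 0.025 and the smallest (0.04) exceeds 0.0167, so none is rejected.

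**The case against.** The strongest reply is that the SAP already resolves this. Section 7 concerns missing data, whereas 12.6.2 is the dedicated testing section. It gives each secondary its own goal, takes over the primary method only for imputation ("Hypothesis testing for the secondary endpoints will be performed in the same manner described for the primary endpoint with respect to multiple imputation"), and then compares the lower bound with the stated goal. The specific rule would normally govern. That is the better reading, and it limits the weight of the point. It does not remove the conflict. No clause gives 12.6.2 precedence, 12.6.1 sends the reader to 7.1 for the regression and pooling, and 8.3 sends the secondary endpoints there for imputation. A programmer working from 7.1 would find method and threshold together.

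On the p-value, SAP 12.6.2.1 does speak of comparing each endpoint with its performance goal, so the intended null can be inferred. A mismatch would be a coding slip that the text does not prevent, not a second contradiction. This part is a clarification.

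On size, the exact figures at n = 89 are the least favourable case. The SAP's method is nearer the logit Wald, and because missing outcomes are imputed the analysed number would be nearer 105. On that basis the fall is from about 90% to about 62%. This is fair, and it is why the result is given as a range.

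**Conclusion.** The concern holds. The success sentence in SAP 7.1 is wrong as written for the PPIUS/voids endpoint and only for that one; 45% is the goal used everywhere else and the one behind the sample size. Applied literally at a true rate of 61%, it would cut power from about 85–90% to about 49–62%.

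The figures are complete-data calculations at an unadjusted two-sided 0.05. They do not model the pooled imputation variance or the Hochberg step, so the decimals are approximate. The contradiction itself does not depend on them. The harm arises only if 7.1 is followed over 12.6.2. It would cost power on one secondary endpoint, would not raise false positives, and would leave the primary endpoint and the overall trial success criterion untouched. It should be fixed before results are known, so that the choice of threshold cannot appear to follow the data.

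**What to change.** Reword the success sentence in SAP 7.1 so that an endpoint succeeds if the lower confidence limit exceeds the performance goal stated for it in Section 12.6: 50% for the primary, HRQL and 12-month responder endpoints, 45% for the PPIUS/voids endpoint.

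Add one sentence, in 7.1 or 12.6.2.1, that for the PPIUS/voids endpoint the pooled intercept is tested against logit(0.45) = −0.201 rather than zero, so that the p-value entering Hochberg agrees with the confidence limit.

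The cost is two sentences in the SAP. Sample size, data collection and the primary analysis do not change.

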10.8.2 Lost-to-Follow-up

Site personnel should make all reasonable efforts to locate and communicate with subjects at each contact time point. If there is difficulty contacting the subject, a minimum of two attempts to contact the subject should be documented. If the subject misses two consecutive scheduled study visit time points and the above-mentioned attempts at communicating with the subject are unsuccessful, and the subject is known to be alive the subject will be considered as "consent withdrawal". If the patient's vital status cannot be confirmed the subject will be considered "lost-to-follow-up". If the reason for discontinuation from the study was made clear by the patient, then it should be documented in the CRF accordingly.

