6.1.2 One-month Responders (OR1)

The one-month responder analysis set (OR1) will be a subset of ITT of subjects who are classified responders in urinary incontinence at one month, defined as \geq 50% reduction from baseline to one-month in average number of urgency-related leaks/day (urinary incontinence).

Percent reduction is defined as it is for the primary endpoint (see section 7.2, below) as related to the 3-day diary collected at the one-month follow-up. For the purposes of the OR1 population, all available diary data will be used (including partial data).

7 Handling of missing data

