8.2 Primary Efficacy Endpoints

Document ID	Revision / Date	Page
G02-CLP-0009	Rev. 06 / 18 May 2022	12 of 26

The study's primary efficacy endpoint for each subject is response at 6 months post system activation as demonstrated by ≥50% improvement in the average number of urgency-related incontinence episodes as compared to baseline, measured by 7-day Patient Voiding Diary. Specifically, the primary endpoint will be defined as follows:

Success ("1") If the percent change from baseline to 6 months post system

activation in urgency-related incontinence episodes ≥50%

Failure ("0") Otherwise

Where the percent change from baseline to 6 months post system activation in urgency-related incontinence episodes is calculated as follows:

Document ID	Revision / Date	Page
G02-CLP-0009	Rev. 06 / 18 May 2022	13 of 26

$$\% \ Change_{BL \ to \ 6-months} = \frac{Episodes_{Avg. \ at \ BL} - \ Episodes_{Avg. \ at \ 6-months}}{Episodes_{BL}} * 100\%$$

where the average number of episodes is the average number of urgency-related leaks per day over the 7- day voiding diary. In the case that fewer than 5 days of diary data are available, then the average number of episodes for the given time point will be considered missing and, consequently, the primary endpoint will also be considered missing.

For the primary efficacy analysis, missing data will be addressed using the multiple imputation (MI) method, described above (Section 7.1).

Note: continuous score will be MI-imputed, and then the response is defined.

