12.6.3 Additional Efficacy Analysis

The additional efficacy endpoints will be assessed descriptively on the ITT, PP and OR1 populations. Descriptive statistics will be provided for diary parameters collected within the Axiom data management report and will include the following by visit for each diary period available:

- Patient Global Impression of Improvement (PGI-I) score
- Treatment Benefit, Satisfaction, and Willingness to Continue (BSW)
- Improvement in OABq (HRQL (and its subscales) and symptoms severity)
- Changes in the following OAB symptoms as measured by voiding diary 6 and 12-months post system activation compared to baseline:
- Reduction in the average number of severe/large urgency related incontinence episodes
- Reduction in the number of micturition episodes.
- Reduction in the number of nocturia episodes.

Document ID	Revision / Date	Page
G02-CLP-0009	Rev. 06 / 18 May 2022	22 of 26

- Reduction in the number of urgency related incontinence episodes.
- Reduction in degree of urgency prior to void on Patient Perception of Intensity of Urgency Scale (PPIUS) from 0-4.
- Reduction in severity of incontinence episodes (amount leaked).
- Proportion of dry subjects following treatment with the RENOVA iStim System as measured by 3
 consecutive days of a patient voiding diary.
- Assessment of fecal incontinence symptoms in patients suffering from mixed fecal and urine incontinence.
- Device usage
- Patient compliance with treatment through 6-months
- Descriptive statistics of percent compliance with treatment will be presented by center and visit.

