12.7 Sensitivity Analysis

To evaluate robustness of the study's primary outcome, an alternative imputation methodology will be examined to assess sensitivity. The primary analysis will utilize multiple imputation.

Tipping Point Imputation

Different proportion of subjects with missing data will be imputed best or worst imputation progressively until the tipping point is reached; i.e. missing cases will be progressively imputed "failure" until the primary analysis is no longer significant (the tipping point).

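### The ITT multiple imputation uses baseline covariates only and ignores the month-1 and month-3 diaries, so the primary rate can be biased in either direction if missingness depends on early response

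*SAP*

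**What the plan says.** SAP 7.1 splits subjects with missing data into two groups. Those missing because of a related adverse event, an explant, lack of effect with a significant rise in UUI medication, or other third-line therapy are scored as failures. The list is introduced as inclusive, so others may join it. All remaining missing values go to multiple imputation (MI), and "The imputation procedure will be performed on the continuous outcomes", with response derived afterwards.

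The covariates are "Age, BMI, average number of urgency leaks, average number of urgent voids, HRQL score and OAB duration at baseline". The only change foreseen is a shorter list: "This list might be reduced if the model fails to converge". Protocol 13.3 likewise names only baseline variables. The SAP does not name the imputation scale.

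Subjects outside the listed failure reasons include:
- those covered by SAP 8.2: "In the case that fewer than 5 days of diary data are available", the endpoint is missing;
- those lost to follow-up;
- those who stop attending without a stated reason. Under Protocol 10.8.2, after two missed visits and failed contact, "and the subject is known to be alive the subject will be considered as" having withdrawn consent.

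Protocol 11.4.5 schedules 3-day diaries at months 1 and 3. SAP 6.1.2 already uses the month-1 diary to define OR1, through the "reduction from baseline to one-month in average number of urgency-related leaks/day". The descriptive summaries in SAP 12.6.3 "will include the following by visit for each diary period available". No section brings these values into the ITT imputation.

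**The concern.** SAP 7.1 acknowledges that MI assumes data missing at random. That assumption may hold given baseline plus the early diaries, yet fail given baseline alone. The usual reason is that a subject's early result affects whether she returns at month 6. The early leak count is also likely to be the best available predictor of the month-6 count.

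Omitting it gives missing subjects roughly the completers' response rate at the same baseline. Success is declared when the lower confidence limit exceeds 50% (SAP 12.6.1). Upward bias near the goal therefore raises the chance of false success, and downward bias costs the sponsor power. If missingness is unrelated to response, there is no bias by this route.

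**Working it through.** **The plan's own figure.** An exact binomial test with n = 114 needs 68 responders: one-sided alpha 0.0244, power 0.9015 at 65%. Then 114/0.85 = 134.1. The 114 and 134 reproduce at 90% power.

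**Inputs from the plan.** N = 150, response 65%, goal 50%, and attrition of up to 15% taken as a ceiling (0.15 × 150 = 22.5 missing).

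**Assumed inputs, not in the documents.** Missingness differs 3.6-fold by month-3 response. The month-3 to month-6 correlation of log change is about 0.7. Among missing subjects, 70% have both early diaries, 20% month 1 only and 10% neither.

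**Closed-form check** (65% response at each visit, bivariate normal, correlation 0.7)

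1. Month-6 response is 0.820 in month-3 responders and 0.334 in non-responders. Check: 0.65 × 0.820 + 0.35 × 0.334 = 0.65.
2. If non-responders are missing more often, the responder missing rate is 0.15/(0.65 + 0.35 × 3.6) = 0.0785. Missing: 97.5 × 0.0785 = 7.7 responders and 52.5 × 0.2827 = 14.8 non-responders.
3. Completers respond at (89.84 × 0.820 + 37.66 × 0.334)/127.5 = 0.6765. Baseline-only MI gives the missing about this rate, so the error is 67.65 − 65 = **+2.65 points**.
4. Suppose the failure rule catches a share of the 14.8 non-responders. They count as failures in both target and estimate. At 25%, k = 3.71: target 0.65 − 3.71 × 0.334/150 = 0.6417; estimate 0.6765 × 146.29/150 = 0.6598; error +1.8. At 50% it is +1.0 and at 75% +0.1.
5. If responders are missing more often (19.6 against 2.9), completers respond at 0.631: error **−1.9**. Equal missingness gives 0.0.
6. With correlation 0.5 or 0.85, the upward error is +1.8 or +3.5 and the downward −1.3 or −2.5.

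**Simulation.** Skewed baseline counts of at least 9 leaks per 7 days, Poisson diaries, six baseline covariates, 20 imputations, response derived after imputation, and logits pooled by Rubin's rules. There were 1,000 trials per bias scenario (Monte Carlo SE at most 0.06 point). Failure-rule subjects count as failures. Errors in points at 15% missing:

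| Pattern (share of missing early non-responders caught) | Log, baseline only | Log, with diaries | PMM, baseline only | PMM, with diaries |
|---|---|---|---|---|
| Non-responders missing more (0%) | +2.0 | +0.1 | +2.4 | +0.8 |
| Same (25%) | +1.3 | +0.1 | +1.6 | +0.5 |
| Same (50%) | +0.6 | −0.1 | +0.8 | +0.2 |
| Unrelated to response | −0.5 | −0.4 | −0.1 | −0.2 |
| Responders missing more | −2.4 | −0.8 | −2.0 | −0.9 |

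PMM is predictive mean matching.

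- **Smaller inputs (log, baseline only).** A 2-fold ratio with no capture gives +0.9 (−0.1 with diaries). With 10% missing: +1.2 and −1.5. With 5%: +0.7 and −0.7.
- **Subjects without diaries.** If half of the missing have none, the fix leaves +0.9 of +2.1. If all have none, it changes nothing.
- **Raw-count normal model.** When non-responders are missing more, baseline-only gives −1.1 to −0.5, and −1.3 with diaries. When responders are missing more: −4.6, then −3.3.

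**Decision effect (log, 15% missing).** With complete data 88 of 150 are needed: logit(88/150) − 1.96 × √(1/88 + 1/62) = 0.025 > 0, whereas 87 gives −0.001.

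| Success declared | Complete data | Baseline only | With diaries |
|---|---|---|---|
| Target 50%, non-responders missing more (0 / 25 / 50% caught) | 2.0% | 5.7 / 4.6 / 3.2% | 1.9 / 2.7 / 2.3% |
| Target 50%, responders missing more | 2.0% | 0.4% | 1.3% |
| True 60%, non-responders missing more (0% caught) | 66% | 79% | 64% |
| True 60%, responders missing more | 66% | 38% | 56% |

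At a true 65%, complete data succeed in 96% of trials. Baseline-only success on log or PMM is 91–99% when non-responders are missing more. When responders are, it is 83–85%, against 91–92% with diaries.

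**Second simulation, separate inputs.** Log change, correlation 0.6, missingness log-odds shifting by 1 per SD of month-3 change, 15% missing. At a true 65%, baseline-only MI gave 68.2% or 62.2% by direction, and 65.2% or 65.0% with diaries. At a true 50%, success was declared in 8.1% or 0.2% of runs, against 1.7% or 1.5%.

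**The case against.** **The upward bias depends on a scale the SAP does not name.** Imputing the number of episodes most literally means raw counts. On that scale the simulation shows no upward bias, and adding diaries alone does not help when non-responders are missing more. This stands. The raw-count model reads low because it fits skewed counts badly, which masks the upward route. The scale must therefore be fixed together with the covariates.

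**The inputs are unfavourable and not from the documents.** The 15% is a ceiling that also covers failure-rule subjects. A 2-fold ratio, 5% missing or substantial capture by the failure rule brings the error below one point. The rule does catch part of the likeliest upward route, but lack of effect on its own is not among the listed reasons.

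**Retention measures and missingness unrelated to response.** Reminder calls, phone or virtual visits and out-of-window visits (Protocol 11.4) should limit missing data, and pandemic-related losses are plausibly unrelated to response. Both reduce the size of the problem without removing it.

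**The pilot gives no support.** Both pilot exits came before activation and one was an explant (Protocol 7.2). Early diaries could not have helped, and the pilot gives no estimate of this bias.

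**The plan already tests the assumption.** In SAP 12.7, "Different proportion of subjects with missing data will be imputed best or worst imputation progressively until the tipping point is reached". That analysis, the observed rate and the per-protocol analysis show how fragile the result is. None of them corrects the primary estimate or uses the early diaries.

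**Conclusion.** The concern holds. The primary imputation leaves out collected data that probably predict both the month-6 count and whether it is missing. The resulting bias can go either way. It is about 2 points at 15% missing with strong selection on a log or PMM scale, and about 0.7 point at 5% missing on the log scale. It is absent by this route if missingness is unrelated to response.

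The upward case matters mainly near the 50% goal; the downward case matters at 60% and still costs some power at 65%. The sizes rest on assumed selection, correlation and diary availability, so confidence in them is medium. The change should be made, but the design does not fail without it.

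**What to change.** In SAP 7.1, before database lock:

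- Add month-1 and month-3 average urgency leaks per day to the imputation model for the month-6 leak endpoint, and impute intermittent missing diaries in the same model. State how partial 3-day diaries are used; SAP 6.1.2 allows partial data for OR1 only.
- For the month-12 leak endpoint, add the available earlier-visit leak values. The reasoning is the same, but this was not simulated.
- State the imputation scale: log or predictive mean matching, not a normal model on raw counts.
- State that the diary variables are not the first to be dropped if the list is reduced.
- Leave the failure rule and the tipping-point analysis unchanged.

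The cost is SAP wording, a few lines of code and a slightly more complex model. No new data or visits are needed, and the permissive wording of Protocol 13.3 leaves room for it. Nothing is gained for subjects who leave before month 1.
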